Using PASS 11 program for sample size calculation ; setting power at 80% , error at 5%, incidence of hypotension among patients undergoing general anesthesia at 78.43% (**Omar et al.,2023**), and sensitivity and specificity of ultrasound guided Aorto-Caval index (IVC-AO) for prediction post general anesthesia hypotension at 77.5% and 63.6% , respectively, (**Omar et al.,2023**) , so a sample size of 32 patients undergoing craniotomy surgeries under general anesthesia will be needed.

Assuming that a drop out is of 10% , a sample size of at least 36 patients undergoing craniotomy surgeries under general anesthesia will be needed.

- **Ethical Consideration:**

- Approval from the research Ethics committee of faculty of medicine ,Ain shams university is mandatory and will be obtained before start in this study.
- Obtaining an informed consent: Written signed and dated informed consent will be obtained from patients or legal guardian of each participant before being entered into the study.
- Patients can withdraw from the study at any time and still get the full medical service within the facility. patients can refuse to participate and still get the standard care.
- Patients, privacy and confidentiality with the right to know the research results are ensured.

- **Sample size:** 40 cases

- **Study Tools:** Ultrasound curvilinear array, low - frequency (2- 5 MHz)

- **Study Procedure**

Pre-operative: All patients will be subjected to:

1- Detailed medical history taking with special emphasis on:

- History of cardiac disease or anti-hypertensive medications.
- Demographic data (age, sex, weight, height, body mass index).

2- Thorough clinical examination including:

- General and local examination.
- American Society of Anesthesiologists (ASA) physical status classification.

3- Laboratory investigations:

- Complete blood picture (CBC).
- Prothrombin time (PT), INR and activated partial thromboplastin time (aPTT).

- Liver functions tests.
- Cardiac enzymes.
- Kidney function tests.

4- Electrocardiogram (ECG).

Intra-operative:

- On the day of surgery, pre-operative fasting for 8 hours will be confirmed.
- Upon arrival to the operating room, routine monitors in the form of pulse oximetry, electro-cardiogram and non-invasive blood pressure monitors will be applied. Intravenous line will be secured.
- central venous line and invasive arterial line will be applied.

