- Systolic blood pressure, diastolic blood pressure, MAP, and HR at baseline will be recorded.
- After obtaining informed consent, the patient is placed in the supine position with the head of the bed elevated 30 degrees.
- The ultrasound transducer is placed in the right subcostal position to visualize the IVC.
- The maximum (expiratory) and minimum (inspiratory) IVC diameters are measured.
- The IVCCI is calculated using the following formula:

$$\text{IVCCI} = (\text{maximum IVC diameter} - \text{minimum IVC diameter}) / \text{maximum IVC diameter} * 100$$

- To the left of the IVC, the abdominal aorta is visualized 10 mm above the coeliac trunk.
- The aortic diameter is measured at maximum diameter during systole
- The IVC : Ao index will be derived by taking the ratio of the maximum IVC diameter during expiration and the maximal abdominal aortic diameter during systole.
- The IVC/Ao index is calculated using the following formula:

$$\text{IVC/Ao index} = \text{IVC diameter} / \text{aortic diameter}.$$

- The measurements are repeated three times and the average is calculated.(Finnerty NM, Panchal AR , Boulger C, et al 2017)

- The patients will be induced as per a standard protocol. They will be given midazolam $0.05\text{--}0.1 \text{ mg} \cdot \text{kg}^{-1}$, and fentanyl $2\text{--}3 \text{ } \mu\text{g} \cdot \text{kg}^{-1}$ before

induction. Patients will be induced with propofol $1-2 \text{ mg.kg}^{-1}$, till loss of response to verbal commands. They will then mask ventilated with 100% oxygen and isoflurane 1.0%–1.2%. Atracurium (0.5 mg.kg^{-1}) will be given for muscle relaxation. Three minutes after atracurium, patients will be intubated by performing a gentle and quick laryngoscopy lasting not more than 15 s. In males, 8 mm or 8.5 mm internal diameter endotracheal tube will be used. In females, 7 mm or 7.5 mm internal diameter endotracheal tube will be used. (Chowdhury SR, Datta PK, Maitra S, et al, 2023)

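### Both indices are calculated before an induction given within dose ranges, and nothing withholds them from the person inducing, so the test result may influence the outcome it is meant to predict

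*Protocol*

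**What the plan says.** The primary aim (Protocol, Aim/Objectives) is the accuracy, repeatability and reproducibility of IVCCI and the caval aorta index for predicting hypotension after induction.

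Under Study Procedure, Intra-operative, the steps run in this order: monitors and lines in the operating room, baseline pressures and heart rate, ultrasound of the IVC, the IVCCI formula, the aortic diameter, the IVC/Ao formula, and then "The measurements are repeated three times and the average is calculated". The next step is induction: "The patients will be induced as per a standard protocol". Within it, midazolam (0.05–0.1 mg/kg), fentanyl (2–3 µg/kg), propofol (1–2 mg/kg) and isoflurane (1.0%–1.2%) are all ranges. Propofol is given "till loss of response to verbal commands". Atracurium is a single stated dose.

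Hypotension is MAP under 80% of baseline or under 60 mmHg. MAP is read every minute until skin incision, for at most 15 minutes. The optimal cut-off is to be found from the data.

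The protocol does not say who scans, who induces, who records MAP, or whether any of them is kept unaware of the index.

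**The concern.** In a study of predictive accuracy, the outcome should arise independently of the test result. Here the written order makes the result available before the first induction drug, and the ranges leave the clinician some room to act on it. The Introduction itself lists propofol and fentanyl among the factors for post-induction hypotension and anaesthetic drugs among its causes. It also presents IVCCI as a guide to volume status. A clinician who sees a worrying value thus has a reason to adjust induction and, within the ranges, permission to do so.

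If that happens, sensitivity and specificity describe the index together with the reaction to it. An event averted because the index looked bad is counted as a false positive. The study expects few non-events, so a handful of such patients can move specificity a long way. Who sees the index before induction is a matter of conduct. An analysis plan cannot recover the events that would have occurred.

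**Working it through.** **Inputs (Protocol, Sample Size Calculation).** Power 80%, error 5%, incidence 78.43%, sensitivity 77.5% and specificity 63.6% for IVC/Ao, N = 32, and 10% dropout giving 36.

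**The plan's own figure.** The protocol concludes "so a sample size of 32 patients undergoing craniotomy surgeries under general anesthesia will be needed". It states no null value. With an assumed null sensitivity of 0.50 and two-sided 5%, 32 × 0.7843 ≈ 25 hypotensive patients. The exact binomial test rejects at 18 or more of 25 (upper tail 0.0216) with power 0.818 at 0.775. Conversely, 25 / 0.7843 = 31.9, so 32. For dropout, 32 / 0.9 = 35.6, so 36. The figure reproduces, and this point does not dispute it.

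**Expected table at N = 32.**
- Events: 32 × 0.7843 = 25.10. Non-events: 6.90.
- True positives (TP): 25.10 × 0.775 = 19.45. False negatives (FN): 5.65.
- True negatives (TN): 6.90 × 0.636 = 4.39. False positives (FP): 2.51.

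**Scenario A: a positive index leads to action that averts hypotension in a share f of true positives.** The cut-off is held fixed, and f is an assumption that the protocol does not supply.

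Sensitivity = TP(1 − f) / (events − f·TP); specificity = TN / (non-events + f·TP).

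At f = 10%: f·TP = 1.95; sensitivity = 17.51 / 23.15 = 75.6%; specificity = 4.39 / 8.85 = 49.6%.

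| f (assumed) | Patients moved | Sensitivity | Specificity |
|---|---|---|---|
| 0 | 0 | 77.5% | 63.6% |
| 5% | 1.0 | 76.6% | 55.7% |
| 10% | 1.9 | 75.6% | 49.6% |
| 20% | 3.9 | 73.4% | 40.7% |

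**Scenario B: a reassuring index leads to a less cautious induction and hypotension in 10% of true negatives.** 0.44 patients move. Sensitivity = 19.45 / 25.54 = 76.2%; specificity = 3.95 / 6.46 = 61.1%.

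**Scenario C: the clinician reacts to IVCCI, and this averts hypotension in 10% of patients who are false negatives on IVC/Ao.** 0.56 patients move. Sensitivity = 19.45 / (25.10 − 0.56) = 79.3%; specificity = (4.39 + 0.56) / (6.90 + 0.56) = 66.4%. Here both measures rise, so the direction is not fixed either.

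These are expected proportions and do not depend on N. Concealing the index leaves the sample size at 32, or 36 with dropout.

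**The case against.** The strongest reply is that the protocol is silent on who knows the index and never says that the inducing clinician is told. The bullets are not a strict timetable: consent is mentioned after the invasive lines, and the formulas define the indices without timing the calculation. Calculation away from the bedside is not excluded. All of this stands, and it makes the bias a risk. It does not remove the risk, because the listed order puts the measurement steps before induction and no sentence withholds the result.

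Three stronger readings are tempting but unsupported:
- **That one team scans, induces, reads MAP and treats.** No role is assigned anywhere.
- **That a high-risk index leads to earlier vasopressor support.** The written ephedrine rule starts only once the hypotension definition is met, so treatment under that rule cannot avert the first episode.
- **That the true-positive to false-positive shift is what the study would report.** The cut-off is derived afterwards, so the table would be re-cut on the affected data. The shifts hold only at a fixed cut-off. A clinician needs no formal cut-off to react to an extreme value, however.

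The room for reaction is also narrower than four ranges suggest. Propofol has a clinical endpoint, the isoflurane range is small, and atracurium and the time to intubation are set. What remains is mainly midazolam and fentanyl. The numeric MAP threshold limits bias in reading the outcome, but it does not stop induction from changing MAP.

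Finally, sampling error is large. With 6.9 non-events the approximate 95% half-width for specificity is 1.96 × √(0.636 × 0.364 / 6.9) = 36 points, more than any shift in the table (8 to 23 points). That is fair as to precision. But averaging over more patients shrinks noise and leaves bias in place.

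**Conclusion.** The point holds as a risk of bias that the written order creates and the protocol does not close. Its size and direction cannot be derived from the document. The main illustration, specificity from 63.6% to 49.6% and sensitivity from 77.5% to 75.6%, rests on an assumed 10% of true positives averted (about 2 of 32 patients). It covers IVC/Ao only, because the protocol gives no accuracy figures for IVCCI, and it assumes a fixed cut-off. It shows how fragile specificity is with about 7 non-events; it does not forecast the result. A reader might infer that the estimates are certain to be biased, or biased downwards. The documents support neither. The change is worth making before enrolment because it is cheap and the damage cannot be repaired in analysis.

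**What to change.** Amend the Intra-operative procedure as follows:
- At the scan, acquire and store three separate IVC and aortic loops. They should be separate acquisitions: three caliper readings on one loop would leave out acquisition variability, and repeatability is part of the primary aim.
- Make the caliper measurements and calculate IVCCI and IVC/Ao only after the last blood-pressure reading (skin incision or 15 minutes).
- State that images and values are not available to the person titrating induction until then.
- Record the induction doses actually given, so that any relation between dose and index can be examined.

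The cost is image storage and later measurement. No extra procedure is needed, the sample size stays the same, and no dose or treatment rule changes. The limitation is that whoever scans still forms a visual impression, so concealment is only partial if that person also induces. The protocol should say whether that is the case.

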The etiology of intra-operative hypotension is multifactorial. Intra-operative hypotension can, among other factors, be caused by vasodilation (anaesthetic drugs, systemic inflammation), intravascular hypovolaemia (bleeding), low cardiac output (bradycardia or low stroke volume), high intra-thoracic pressure (mechanical ventilation), impairment of sympathetic nervous system or compromised baroreflex regulation. (**Kouz K, Hoppe P, Briesenick L, et al, 2020**).

With some individual variation, autoregulation of cerebral blood flow (CBF) typically occurs within a mean arterial pressure (MAP) range of 60 to 150 mmHg. Outside of this range, the brain is unable to compensate for changes in perfusion pressure, and the cerebral blood flow (CBF) increases or decreases passively with corresponding changes in pressure, resulting in the risk of ischemia at low pressures and edema or hemorrhage at high pressures. We aim for a MAP above the lower limit of autoregulation. (**Lassen NA**.)

2.AIM /OBJECTIVES

- **Primary aim:** Assessment of the accuracy, repeatability, and reproducibility of preoperative evaluation of IVC collapsibility index and Caval Aorta Index for prediction of hypotension after induction of general anesthesia.
- **Secondary aim:** to compare values of both IVCCI and Aorto-Caval Index in prediction of post general anesthesia induction hypotension.

3.METHODOLOGY:

Subjects and Methods

- **Type of Study:** Prospective cohort study.
- **Study Setting:** the study will be conducted at Ain-Shams University Hospitals.
- **Study Period:** the study will take place till reaching the target sample size.
- **Study Population:**

Selection criteria:

Inclusion Criteria:

- Patients aging 18-40 years.
- $BMI < 40 \text{ kg/m}^2$.
- ASA I, II.
- Fasted according to the ASA guidelines: 2 hours for clear fluids, 6 hours after light meal, 8 hours after a full meal with high calorie or fat content.
- Scheduled for elective craniotomy surgeries before induction of general anesthesia.

- Exclusion Criteria:

- Patients < 18 or > 40 years.
- $BMI > 40 \text{ kg/m}^2$.
- ASA III, IV.
- Current or recent pregnancy (within 3 months).
- Pre-existing cardiac disease or hypertension.
- On medications affecting blood pressure (BBs, CCBs,..).
- Refusing to undergo the study.

- **Sample Size Calculation:**

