- Measurement tools - Mean arterial blood pressure will be measured in supine position in one of the upper limbs in the operating room at 1-minute intervals starting from the baseline preoperative reading until skin incision as follows: 1-minute post-induction reading, 2-minutes post-induction reading, pre-intubation reading & post-intubation readings until skin incision. Taking in consideration that the maximum time for recording the readings of the blood pressure is 15 minutes because if hypotension occurred after this time it is unlikely to be due to the effect of induction of anesthesia.
- Heart rate will be recorded at 1-minute intervals starting from the baseline pre-operative reading until skin incision as follows: 1-minute post-induction reading, 2-minutes post-induction reading, pre-intubation reading & post-intubation readings until skin incision. Any episode of hypotension (defined as mean arterial pressure $< 80\%$ of the baseline reading or MAP less than 60 mmHg) will be managed by ephedrine 5 mg every 2 min to increase SBP to 80% of the baseline or MAP more than 70 mmHg. If the hypotensive episode persisted for 2 minutes, another bolus of norepinephrine will be administered.
- The strength of the association between different parameters and post-anesthesia hypotension was calculated. To find out the value of the optimal cut-off for the prediction of post-anesthesia hypotension.

● Statistical Method:

Data collection: Demographic, clinical data, investigations, imaging, ECG and echocardiographic data will be obtained and recorded in special registration form.

Statistical analysis:

Statistical data will be tabulated, and Statistical analysis is to be performed using the latest available version of SPSS.

4. REFERENCES:

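### The ephedrine goal does not mirror the hypotension definition: either branch can be met while MAP still counts as hypotensive

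*Protocol*

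**What the plan says.** The rule stands in the protocol, section 3 (Methodology), Study Procedure, in the heart-rate bullet that follows the one on measurement tools.

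- **Definition and trigger.** The sentence opens "Any episode of hypotension (defined as mean arterial pressure", sets the relative limit at below 80%, and continues "of the baseline reading or MAP less than 60 mmHg". Both limbs are in MAP.
- **Treatment goal.** The same sentence says that an episode "will be managed by ephedrine 5 mg every 2 min to increase SBP to 80% of the baseline or MAP more than 70 mmHg". The relative limb is now in systolic pressure (SBP), the absolute limb is in MAP at a different value, and the two are joined by an unexplained *or*.
- **Escalation.** The next sentence reads: "If the hypotensive episode persisted for 2 minutes, another bolus of norepinephrine will be administered".
- **What is recorded.** "Mean arterial blood pressure will be measured in supine position in one of the upper limbs in the operating room at 1-minute intervals", with heart rate alongside. SBP is listed for recording at baseline. It is not among the serial readings, although an arterial line is planned ("central venous line and invasive arterial line will be applied") and would display it.
- **Stated pressure aim.** The last paragraph of section 1 says that cerebral autoregulation "typically occurs within a mean arterial pressure (MAP) range of 60 to 150 mmHg" and adds: "We aim for a MAP above the lower limit of autoregulation".

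Nothing elsewhere in the protocol reconciles the goal with the definition.

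**The concern.** A rule that starts treatment on one criterion and stops it on another can call the goal reached while the patient still meets the criterion that started treatment. Here that can happen through either branch of the goal.

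The practical question is when ephedrine stops and when an episode counts as persisting, so that norepinephrine is due. As written, the ephedrine goal can be met and the episode can persist at the same minute. These are craniotomy patients, and the protocol says that it wants MAP above the lower limit of autoregulation. A goal in SBP does not by itself secure that.

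**Working it through.** **Inputs.** From the protocol: hypotension is MAP < 0.8 × baseline MAP or MAP < 60; the goal is SBP at 0.8 × baseline SBP, or MAP > 70. The protocol gives no baseline pressures, so 100/60, 110/70, 120/80 and 130/85 are assumptions. MAP is approximated as (SBP + 2 × DBP)/3. The plan states no figure of its own to reproduce on this point.

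**1. SBP branch, general condition.** With SBP exactly at 80% of its baseline, MAP = (0.8 × SBP₀ + 2 × DBP)/3. This is below 0.8 × MAP₀ exactly when DBP < 0.8 × DBP₀, that is, when diastolic pressure has fallen proportionally more than systolic.

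**2. SBP branch, proportional fall.** If both pressures fall by 20%, MAP is exactly 80% of baseline. There is no gap when baseline MAP is at least 60/0.8 = 75 mmHg. Below that, the 60 mmHg limb is still met: 100/60 has baseline MAP 73.3, and 80/48 gives (80 + 96)/3 = 58.7. An 80% goal in MAP would give the same 58.7, so this case shows a missing floor and not a fault of SBP as such.

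**3. SBP branch, pulse pressure unchanged.** The threshold is the higher of 60 and 80% of baseline MAP.

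| Assumed baseline | Baseline MAP | Threshold | Pressure at SBP goal | MAP at goal | Shortfall |
|---|---|---|---|---|---|
| 100/60 | 73.3 | 60.0 (80% = 58.7) | 80/40 | (80 + 80)/3 = 53.3 | 6.7 |
| 110/70 | 83.3 | 66.7 | 88/48 | (88 + 96)/3 = 61.3 | 5.3 |
| 120/80 | 93.3 | 74.7 | 96/56 | (96 + 112)/3 = 69.3 | 5.3 |
| 130/85 | 100.0 | 80.0 | 104/59 | (104 + 118)/3 = 74.0 | 6.0 |

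For the last three rows the shortfall equals (2/3) × 0.2 × baseline pulse pressure: 5.3 for 40 mmHg and 6.0 for 45 mmHg.

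**4. When MAP falls below 60 at the SBP goal.** This needs DBP < (180 − SBP goal)/2.

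- 120/80: DBP below 42, so pulse pressure above 96 − 42 = 54 (baseline 40).
- 130/85: DBP below 38, so pulse pressure above 104 − 38 = 66 (baseline 45).
- 110/70: DBP below 46, so pulse pressure above 88 − 46 = 42 (baseline 40). This is borderline.
- 100/60: already below 60 in steps 2 and 3.

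**5. MAP branch.** A MAP just above 70 is still below 80% of baseline when baseline MAP > 70/0.8 = 87.5. From 120/80 the overlap runs from 70 to 74.7, so a MAP of 71 meets the goal and is still hypotensive. From 130/85 it runs from 70 to 80. From 100/60 and 110/70 there is none, since their thresholds (60.0 and 66.7) lie below 70.

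**6. Check of the remedy.** If the goal is MAP ≥ 0.8 × baseline **and** MAP ≥ 60, it is the exact complement of the definition. No reading can then satisfy both.

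**The case against.** Four arguments on the other side have force.

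- **The next sentence largely deals with it.** The hypotensive episode in the norepinephrine rule most naturally means the episode just defined in MAP. With MAP read every minute, a patient at the SBP goal whose MAP still qualifies would be escalated at 2 minutes. This stands, and it limits the effect. It leaves the conflict between an ephedrine goal that is met and an episode that persists.
- **The lowest figures need one reading of *or*.** If the limbs are paired, a fall below 60 is treated to MAP above 70, and the values below 60 do not meet the applicable goal. The text does not settle which reading is meant, so those figures hold only if either limb suffices.
- **It may be a one-word slip.** SBP may well be a slip for MAP. That is a reason to correct a dosing instruction. It would not be a full cure, because the MAP branch also overlaps the definition.
- **The autoregulation argument is thin.** With pulse pressure unchanged, MAP at the SBP goal stays above 60 for three of the four assumed baselines, though only just from 110/70. This stands.

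A reader might infer two stronger things. One is that the mismatch biases the accuracy results. The documents do not support this: an episode must already have occurred before ephedrine is given, so the yes/no outcome is fixed before the goal comes into play, and the aims name no episode count, duration or vasopressor dose. The other is that patients would be left untreated below the autoregulation limit. That needs a low baseline or a widened pulse pressure, the less favourable reading of *or*, and a norepinephrine step that is not read by the MAP definition.

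**Conclusion.** The point holds as a minor correction for patient safety and consistency: the goal is wrong as written, in both branches. Under the assumed pressures with pulse pressure unchanged, the SBP branch leaves MAP 5.3 to 6.7 mmHg short of the threshold. It leaves no gap if both pressures fall in proportion and baseline MAP is 75 mmHg or more. The MAP branch leaves MAP up to 4.7 mmHg short from 120/80 (74.7 − 70) and up to 10 mmHg short from 130/85 (80 − 70). A MAP below 60 at the SBP goal is mainly a matter of low baselines.

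These sizes rest on the assumed baselines and the one-third formula for MAP. How many patients would reach the goal while still hypotensive cannot be computed from the protocol. The binary endpoint, the sample size and both aims are unaffected.

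**What to change.** Reword the two sentences so that one MAP criterion governs start, stop and escalation:

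- Replace SBP with MAP in the ephedrine goal.
- State that ephedrine continues until MAP is at least 80% of baseline **and** at least 60 mmHg. After a fall below 60 mmHg, keep the protocol's own target of above 70 mmHg in addition to the 80% condition. Both limbs are needed: below a baseline MAP of 75 mmHg, 80% of baseline is itself under 60, and above 87.5 mmHg a target of 70 alone is under 80% of baseline.
- State that the 2-minute norepinephrine rule uses the same MAP criterion.

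The choice of drug and dose stays with the clinical team. The cost is a rewording within one bullet. MAP is already read every minute and an arterial line is already planned, so data collection, endpoint and sample size do not change.

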Protocol of a Thesis for Partial Fulfillment of M.D. degree in Anesthesia

Title:

Preoperative Evaluation of IVC Collapsibility Index and Caval Aorta Index for Prediction of Hypotension after Induction of General Anesthesia in patients Undergoing Craniotomy Surgeries

Postgraduate Student: **[name]**

Degree: *M.B.B.CH- assistant-lecturer in department of Anesthesia, Intensive Care and Pain Management- Faculty of Medicine -Ain Shams University*

Supervisor: **[name]. [name]**

Academic Position: *Professor of Anesthesia, Intensive Care and Pain Management*

Department: *Anesthesia, Intensive Care and Pain Management - Faculty of Medicine Ain Shams University*

Co- Supervisor: **Ass.[name]. [name]**

Academic position: *Assistant Professor of Anesthesia, Intensive Care and Pain Management*

Department: *Anesthesia, Intensive Care and Pain Management - Faculty of Medicine Ain Shams University*

Co- Supervisor: **[name] [name]**

Academic position: *lecturer of Anesthesia, Intensive Care and Pain Management*

Department: *Anesthesia, Intensive Care and Pain Management - Faculty of Medicine Ain Shams University*

Co- Supervisor: **[name] [name]**

Academic Position: *lecturer of Anesthesia, Intensive Care and Pain Management*

Department: *Anesthesia, Intensive Care and Pain Management - Faculty of Medicine Ain Shams University*

**Faculty of Medicine
Ain Shams University
2023**

What is already known on this subject? AND What does this study add?

Intraoperative hypotension has been the most frequent side effect after anesthesia, with an incidence of 15.3% to 33%. Hypotension can be severe (incidence 5.4%) and may cause systemic hypoperfusion and ischemic events. (Jor, O., Maca J., Koutna J., et al.2018)

The caval aorta index (IVC/Ao) compares the maximum diameter of the IVC with the abdominal aorta (Ao).

This study is to assess the accuracy, repeatability, and reproducibility of preoperative evaluation of IVC Collapsibility Index and Caval Aorta Index for prediction of hypotension after induction of general anesthesia.

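### The optimal cut-off is to be found in the same 32–40 patients who supply the primary accuracy result, so sensitivity and specificity reported uncorrected at it would on average be too high, mainly in the smaller outcome group

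*Protocol*

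**What the plan says.** The primary aim (Protocol, 2. AIM/OBJECTIVES) is "Assessment of the accuracy, repeatability, and reproducibility of preoperative evaluation of IVC collapsibility index and Caval Aorta Index for prediction of hypotension". The design (3. METHODOLOGY, Type of Study) is a "Prospective cohort study", and no second cohort for validation is described.

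The Sample Size Calculation plans on "sensitivity and specificity of ultrasound guided Aorto-Caval index (IVC-AO) for prediction post general anesthesia hypotension at 77.5% and 63.6" per cent and on "incidence of hypotension among patients undergoing general anesthesia at 78.43" per cent. It arrives at 32 patients, or 36 with dropout; a later line gives 40 cases. Sensitivity and specificity are the only accuracy figures in the document. Both presuppose a cut-off, but no numerical threshold is stated for the collapsibility index or for the caval aorta index.

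The last bullet of the Study Procedure, just before Statistical Method, states the task: "To find out the value of the optimal cut-off for the prediction of post-anesthesia hypotension". It gives no criterion for optimal. The Statistical Method section mentions only tabulation and the software.

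The opening background section gives a different incidence: "Intraoperative hypotension has been the most frequent side effect after anesthesia, with an incidence of 15.3% to 33" per cent.

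**The concern.** A cut-off chosen because it separates the observed patients best also fits the chance features of that sample. Sensitivity and specificity counted at that cut-off in the same patients carry this gain, so on average they exceed what the same cut-off would achieve in new patients. The excess falls mainly on the smaller outcome group, where each patient moves the proportion most: with 25 hypotensive and 7 non-hypotensive patients, one patient is worth 1/25 = 4 points of sensitivity but 1/7 = 14 points of specificity.

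Accuracy is the primary aim, so the bias would sit in the main result. An index with no predictive value would, on average, look weakly useful.

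**Working it through.** **The planned size.** The protocol states 80% power and 5% error but no null value. Assuming a null sensitivity of 50% and an exact two-sided 5% binomial test, 32 patients give 32 × 0.7843 = 25.1, so 25 hypotensive patients, and the power for a sensitivity of 77.5% is 81.8%. No total from 24 to 31 reaches 80%, so 32 is reproduced. Dropout: 32/(1 − 0.10) = 35.6, so 36. The same test of specificity (63.6% against 50%) with 7 patients has about 4% power. On this reading the size was set by sensitivity alone.

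**Group sizes.** These are N × incidence, rounded, for N = 32 to 40:
- 78.43%: 25/7 to 31/9 (hypotensive/non-hypotensive)
- 33%: 11/21 to 13/27
- 15.3%: 5/27 to 6/34

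**Model (assumed).** Normal index values with equal variance in both groups, and an ROC curve through the planned point: d = z(0.775) + z(0.636) = 1.103; AUC = Φ(d/√2) = 0.78. In each of 10,000 simulated cohorts per case the cut-off maximises sensitivity + specificity (Youden). Apparent values are then compared with the model's true values at that same cut-off.

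Results with the cut-off midway between observed values (apparent vs true; J = sensitivity + specificity − 1):

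| Groups | Sensitivity | Specificity | J | J, useless index (true 0) |
|---|---|---|---|---|
| 25/7 | 0.750 vs 0.709 | 0.821 vs 0.666 | 0.571 vs 0.375 | 0.233 |
| 31/9 | 0.749 vs 0.712 | 0.803 vs 0.668 | 0.552 vs 0.380 | 0.211 |
| 13/27 | 0.795 vs 0.695 | 0.740 vs 0.691 | 0.535 vs 0.386 | 0.188 |
| 6/34 | 0.829 vs 0.654 | 0.747 vs 0.718 | 0.576 vs 0.372 | 0.244 |

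At 25/7 the excess is 0.821 − 0.666 = 15.5 points for specificity and 0.750 − 0.709 = 4.1 points for sensitivity. With the cut-off placed at an observed value it is 0.822 − 0.687 = 13.5 and 0.747 − 0.690 = 5.7 points. The Monte Carlo standard error of the excess in J is at most 0.002. These are averages: at 25/7, apparent specificity exceeds its true value in 85–88% of runs and apparent sensitivity in 71–76%.

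**Dependence on the assumptions.** A second simulation let the number of hypotensive patients vary at random. Specificity excess at 78.43% incidence, in points:

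| Criterion | N = 32 | N = 36 | N = 40 |
|---|---|---|---|
| Youden | 16.6 | 15.3 | 14.6 |
| Closest to corner | 13.6 | 12.5 | 11.9 |
| Maximum accuracy | 12.0 | 11.1 | 10.4 |

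The sensitivity excess was 3.0–4.0 points throughout. With a Youden cut-off, N = 36 and true AUC from 0.50 to 0.92, the excess was 12.3–18.3 points for specificity and 2.9–4.8 for sensitivity. At an incidence of 50% it was 7.5 points each. A cut-off fixed in advance carries no such excess.

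**Does correction work?** Average J over 700 runs, midway cut-off:

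| Case | Apparent | True | Bootstrap-corrected | Leave-one-out | Repeated 5-fold |
|---|---|---|---|---|---|
| 25/7 | 0.564 | 0.374 | 0.452 | 0.366 | 0.361 |
| 31/9 | 0.556 | 0.381 | 0.454 | 0.369 | 0.380 |
| 13/27 | 0.529 | 0.384 | 0.436 | 0.375 | 0.371 |
| 6/34 | 0.572 | 0.372 | 0.459 | 0.346 | 0.354 |
| 25/7, useless index | 0.237 | 0 | 0.107 | 0.007 | 0.005 |

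Cross-validation comes close to the truth. The bootstrap optimism correction removes only part of the excess: at 25/7, (0.564 − 0.452)/(0.564 − 0.374) = 59%, and 55–64% over the five rows.

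**The case against.** The strongest reply is that the protocol does not say uncorrected sensitivity and specificity will be the primary result. It says only accuracy. The AUC would satisfy that word and does not depend on a cut-off. The accuracy measure, the criterion for optimal and any internal validation are ordinary content of an analysis plan that is not at hand. Looking for a threshold in one cohort is also legitimate development work, and the protocol does not claim the result is validated.

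Part of this stands. The harm is conditional on how the figures are reported, and an analysis plan with cross-validation would largely remove it. But the point does not rest on missing detail. The protocol itself derives the cut-off in its only cohort, makes accuracy the primary aim, and plans solely on sensitivity and specificity.

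The size also depends on choices the protocol does not make. Criteria other than Youden give a smaller excess, although the direction held in every setting tried. The 15.3–33% incidences are background figures with no definition of hypotension attached, so they show a range and are not planning values. Finally, sampling error exceeds the bias: 5 of 7 correct is 71% with an exact 95% interval of 29–96%. That is true, but a wide interval does not excuse centring it on an optimistic estimate.

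**Conclusion.** The concern holds: carried out as written and reported without correction, the plan overstates accuracy on average.

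- **Planning incidence (78.43%), Youden cut-off, fixed group sizes:** specificity +12 to +16 points, sensitivity +4 to +6. Over the three criteria and random group sizes, specificity is overstated by about 10–17 points.
- **Incidence 33%:** the bias moves to the hypotensive group, with sensitivity +10 to +13 points and specificity +4 to +6.
- **Incidence 15.3%:** sensitivity +17 to +21 points, specificity +2 to +4.
- **Useless index (Youden):** average Youden index of about 0.19–0.27 across these cases, against a true 0.

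The sizes rest on the equal-variance binormal model and on the selection criterion. The direction, and the concentration in the smaller group, do not depend on which criterion or AUC was tried. The AUC is not affected. This should be changed, but it does not invalidate the study.

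**What to change.** 1. Name the AUC with a 95% confidence interval, for each index, as the primary accuracy measure.
2. Label the data-derived cut-off exploratory. Report its sensitivity and specificity from leave-one-out or repeated stratified 5-fold cross-validation, re-selecting the cut-off each time without the left-out patients, with 95% confidence intervals. State the selection criterion. A bootstrap optimism correction is better than none but leaves a good part of the excess.
3. If the sponsor can state a cut-off before any outcome data are examined, for example one from the planning source (whose value the protocol does not give), also report sensitivity and specificity with exact 95% intervals at that fixed value.

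The cost is a few lines of text and a short script; leave-one-out needs 32–40 re-selections per index. No extra patients or measurements are needed. Reported accuracy will look less favourable. The change does not cure the imprecision in the smaller group: 6 of 9 correct, for example, is 67% with an exact 95% interval of 30–93%.
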